6.12.4.1. Hepatic Laboratory Examinations

Analyses for change from baseline to last observation, change from the minimum value during the baseline period to the minimum value during the treatment period, change from the maximum value during the baseline period to the maximum value during the treatment period, and treatment-emergent high or low laboratory results at any time are described in Section 6.12.4. This section describes additional analyses for the topic.

The percentages of patients with the following elevations in hepatic laboratory tests at any time will be summarized between treatment groups:

- The percentages of with a alanine aminotransferase (ALT) measurement greater than or equal to 3 times (3X), 5 times (5X), and 10 times (10X) the Covance upper limit of normal (ULN) during the treatment period will be summarized for all patients with a postbaseline value and for subsets based on various levels of baseline.
 - The analysis of 3X ULN will contain 4 subsets:
 - patients whose non-missing maximum baseline value is less than or equal to 1X ULN,
 - patients whose maximum baseline is greater than 1X ULN but less than 3X ULN,

- patients whose maximum baseline value is greater than or equal to 3X ULN, and
- patients whose baseline values are missing.
- The analysis of 5X ULN will contain 5 subsets:
 - patients whose non-missing maximum baseline value is less than or equal to 1X ULN,
 - patients whose maximum baseline is greater than 1X ULN but less than 3X ULN,
 - patients whose maximum baseline is greater than or equal to 3X ULN but less than 5X ULN,
 - patients whose maximum baseline value is greater than or equal to 5X ULN, and
 - patients whose baseline values are missing.
- The analysis of 10X ULN will contain 6 subsets:
 - patients whose non-missing maximum baseline value is less than or equal to 1X ULN,
 - patients whose maximum baseline is greater than 1X ULN but less than 3X ULN,
 - patients whose maximum baseline is greater than or equal to 3X ULN but less than 5X ULN,
 - patients whose maximum baseline is greater than or equal to 5X ULN but less than 10X ULN,
 - patients whose maximum baseline value is greater than or equal to 10X ULN, and
 - patients whose baseline values are missing.
- The percentages of patients with an AST measurement greater than or equal to 3 times (3X), 5 times (5X), and 10 times (10X) the Covance upper limit of normal (ULN) during the treatment period will be summarized for all patients with a postbaseline value and for subsets based on various levels of baseline. Analyses will be constructed as described above for ALT.
- The percentages of patients with a total bilirubin measurement greater than or equal to 2 times (2X) the Covance upper limit of normal (ULN) during the treatment period will be summarized for all patients with a postbaseline value, and subset into 4 subsets:
 - patients whose nonmissing maximum baseline value is less than or equal to 1X ULN,

- patients whose maximum baseline is greater than 1X ULN but less than 2X ULN,
- patients whose maximum baseline value is greater than or equal to 2X ULN, and
- patients whose baseline values are missing.

Maximum baseline will be the maximum nonmissing observation in the baseline period. The maximum value will be the maximum nonmissing value from the treatment period. Planned and unplanned measurements will be included.

In addition, the percentages of patients with treatment-emergent potentially drug-related hepatic disorders will be summarized by treatment by using the MedDRA preferred terms contained in any of the following SMQs:

- Broad and narrow terms in the Liver related investigations, signs and symptoms SMQ (20000008)
- Broad and narrow terms in the Cholestasis and jaundice of hepatic origin SMQ (20000009)
- Broad and narrow terms in the Hepatitis non-infections SMQ (20000010)
- Broad and narrow terms in the Hepatic failure, fibrosis and cirrhosis and other liver damage SMQ (20000013)
- Narrow terms in the Liver-related coagulation and bleeding disturbances SMQ (20000015).

The percentage of patients with any 1 of the terms will be summarized in addition to the percentages for each MedDRA preferred term. The percentages of patients with potentially drug-related hepatic disorders that led to study medication discontinuation will be summarized similarly.

Individual graphic patient profiles will be prepared for patients with an ALT or AST measurement greater than or equal to 5X ULN or with an alkaline phosphatase measurement greater than or equal to 2X ULN. The graphical profile will be created for any patient meeting the criteria from the safety population (any phase, any medication) The graphical patient profile will include demographics, disposition, and a display of study drug exposure, adverse events, medications, and the liver-related measurements over time. The review for these patients includes an assessment of the proximity of any ALT or AST elevation to any total bilirubin elevation, alkaline phosphatase levels, gamma-glutamyl transpeptidase (GGT) levels, other potential causes, and the temporal association with events such as nausea, vomiting, anorexia, abdominal pain, or fatigue.

6.12.5. Vital Signs and Other Physical Characteristics

Vital signs include systolic blood pressure, diastolic blood pressure, pulse, and temperature. Physical characteristics include weight and body mass index (BMI).

Vital signs and physical characteristics will be summarized and analyzed for the Induction Period only, except where noted.

Other periods may be summarized if appropriate.

Vital sign and physical characteristic results will be provided in a by-patient listing.

BMI will be calculated using the following formula:

$$BMI (kg/m^2) = weight (kg) \text{ divided by the square of the height } (m).$$

Values at each visit (starting at randomization) and change from baseline to each visit for vital signs and physical characteristics will be displayed in box plots (notched box for each treatment with outliers displayed) for patients who have both a baseline and a result for the specified visit. Individual measurements outside of reference limits will also be displayed using distinct symbols overlaying the box plot. Baseline will be the last nonmissing observation in the baseline period. Original-scale data will be used for the display. Unplanned measurements will be excluded. The following summary statistics will be included in a table below the box plot: N, mean, standard deviation, minimum, Q1, median, Q3, and maximum. P-values and confidence limits will not be included in the summary statistics at the bottom of the box plot. Box plots will be used to evaluate trends over time and to assess a potential impact of outliers on central tendency summaries.

Change from baseline to last observation will also be summarized within the box plot of changes (rightmost column) for patients who have both baseline and at least 1 postbaseline result. Baseline will be the last nonmissing observation in the baseline period. The last nonmissing observation in the treatment period will be used as the last observation. Original-scale data will be used. Unplanned measurements will be excluded. No statistical comparisons are planned and only summaries will be produced.

The percentages of patients with treatment-emergent high or low vital signs and physical characteristics results at any time will be summarized. A treatment-emergent high result is defined as a change from a value less than or equal to the high limit at all baseline visits to a value greater than the high limit at any time that meets the specified change criteria during the treatment period. A treatment-emergent low result is defined as a change from a value greater than or equal to the low limit at all baseline visits to a value less than the low limit at any time that meets the specified change criteria during the treatment period. To assess increases, change from the maximum value during the baseline period to the maximum value during the treatment period will be used. To assess decreases, change from the minimum value during the baseline period to the minimum value during the treatment period will be used. [Table 6.4](#) will be used to define the low and high limits and change thresholds. The low/high displays will be created for the Maintenance Period as well, but no statistical comparisons are planned and only summaries will be produced.

Additionally, values at each visit (starting at randomization) and change from baseline to each visit for vital signs and physical characteristics will be displayed in box plots (with outliers displayed) for patients who have both a baseline and a result for the specified visit. Baseline will

be the last non-missing observation in the baseline period. Original-scale data will be used for the display. Unplanned measurements will be excluded. Reference limits will not be displayed. The following summary statistics will be included in a table below the box plot: N, mean, standard deviation, minimum, Q1, median, Q3, and maximum. P-values and confidence limits will not be included in the summary statistics at the bottom of the box plot. Box plots will be used to evaluate trends over time and to assess a potential impact of outliers on central tendency summaries.

Table 6.4. Categorical Criteria for Abnormal Treatment-Emergent Blood Pressure and Pulse Measurement, and Categorical Criteria for Weight and Temperature Changes for Adults

Parameter	Low mmHg	High mmHg
Systolic BP (mm Hg) (Supine or sitting – forearm at heart level)	≤ 90 and decrease from baseline ≥ 20	≥ 140 and increase from baseline ≥ 20
Diastolic BP (mm Hg) (Supine or sitting – forearm at heart level)	≤ 50 and decrease from baseline ≥ 10	≥ 90 and increase from baseline ≥ 10
Pulse (bpm) (Supine or sitting)	< 50 and decrease from baseline ≥ 15	> 100 and increase from baseline ≥ 15
Weight (kg) (Consistent clothing and timing in relationship to meals and voiding)	(Loss) decrease $\geq 7\%$	(Gain) increase $\geq 7\%$
Temperature	< 96 degrees F and decrease ≥ 2 degrees F	≥ 101 degrees F and increase ≥ 2 degrees F

Abbreviations: BP = blood pressure; bpm = beats per minute

6.12.6. Electrocardiograms

Electrocardiogram results will be provided in a by-patient listing.

Complete ECG data will not be part of the clinical database for this study. According to protocol instructions, clinically significant ECG measurements as determined by the investigator should be reported and recorded as an AE. ECG data will not be analyzed.

6.12.7. C-SSRS

Suicidal ideation, suicidal behavior, and self-injurious behavior without suicidal intent, based on the C-SSRS, will be listed by patient and visit. Only patients that show suicidal ideation/behavior or self-injurious behavior without suicidal intent will be displayed (that is, if a patient answers are all ‘no’ for the C-SSRS, then that patient will not be displayed). However, if a patient reported any suicidal ideation/ behavior or self-injurious behavior without suicidal intent at any time point then all their ideation and behavior will be displayed, even if not positive.

6.13. Immunogenicity

Figure 6.1 provides an overview of the immunogenicity assay process.

At a high level, an individual sample is potentially examined multiple times in a hierarchical procedure to produce a sample Anti-Drug Antibodies (ADA) assay result and potentially a sample neutralizing antibody (NAb) assay result. The cut points used, the drug tolerance of an assay, and the possible values of titers are operating characteristics of the assay.

It can be the case that the presence of high concentrations of LY will affect the measurements of the presence of ADA or NAb, and conversely high levels of ADA or NAb may affect the measurement of LY concentration. Thus an LY drug concentration, assessed from a sample drawn at the same time as the ADA sample, plays a key role in clinical interpretation of a sample when the laboratory result is Not Detected, as shown in Figure 6.1.

The rest of this section defines the component concepts of Figure 6.1 in greater detail.

[figure not shown]

Figure 6.1. Flow chart of ADA sample assessment with clinical interpretation.

6.13.1. Definitions of Sample ADA Status

Table 6.5. Sample ADA Assay Results

Sample Laboratory Result	Explanation
Detected	ADA are detected and confirmed.
Not Detected	The raw result as reported from the laboratory indicates not detected. The clinical interpretation of such results depends on other factors (see below).
NO TEST, QNS, etc.	Sample exists but was unevaluable by the assay

Abbreviations: ADA = anti-drug antibodies; QNS = quantity not sufficient

Table 6.6. Sample Clinical ADA Interpretation Results

Sample Clinical Interpretation	Explanation
ADA Present	ADA assay result is Detected
ADA Not Present	ADA assay result is Not Detected and simultaneous drug concentration is at a level that has been demonstrated to not interfere in the ADA detection method (that is, drug concentration is below the assay's drug tolerance level). For patients receiving placebo, drug concentration is not assessed and is assumed to be below the assay's drug tolerance level. If drug concentration was planned but is not available for a treatment-period sample, a Not Detected sample will be declared ADA Not Present, on the basis of prior knowledge that the drug tolerance level of the ADA assay is high relative to peak PK levels.
ADA Inconclusive	ADA assay result is Not Detected but drug concentration in the sample is at a level that can cause interference in the ADA detection method, or drug concentration is planned per protocol but is not available.
ADA Missing	ADA sample not drawn, QNS, not tested, etc., causing there to be no laboratory result reported or the result is reported as "no test".

Abbreviations: ADA = anti-drug antibodies; PK = pharmacokinetic; QNS = quantity not sufficient.

Parallel terminology applies for NAb Detected, NAb Not Detected, NAb Present, NAb Not Present, NAb Inconclusive, and NAb Missing. ADA and NAb are distinct assays and have different assay operating characteristics.

6.13.2. Definitions of Immunogenicity Assessment Periods

Immunogenicity Baseline Observations: Baseline period for immunogenicity assessment for each patient includes all observations on or prior to the date of the first administration of study drug. In instances where multiple baseline observations are collected, to determine patient ADA status, the last non-missing immunogenicity assessment prior to first administration of study drug is used to determine ADA treatment-emergent status (see below). In this context, 'missing' includes explicit 'ADA Missing' results, as defined in [Table 6.6](#).

Immunogenicity Postbaseline Period Observations: Postbaseline period observations for each patient include all observations after the first administration of study drug.

6.13.3. Definitions of Patient ADA Status

Patient evaluable for treatment-emergent ADA: A patient is evaluable for treatment-emergent ADA if the patient has a non-missing baseline ADA result, and at least 1 non-missing postbaseline ADA result.

Treatment-emergent ADA positive (TE ADA+) patient: A patient who is evaluable for treatment-emergent ADA is TE ADA+ if either of the following holds:

- a. The patient has baseline status of ADA Not Present and at least 1 postbaseline status of ADA Present with titer $\geq 2 * \text{MRD}$, where the MRD is the minimum required dilution of the ADA assay.
- b. The patient has baseline and postbaseline status of ADA Present, with the postbaseline titer being 2 dilutions (4-fold) greater than the baseline titer. That is, the patient has baseline status of ADA Present, with titer 1:B, and at least 1 postbaseline status of ADA Present, with titer 1:P, with $P/B \geq 4$.

Treatment-emergent ADA Inconclusive patient: A patient who is evaluable for TE ADA is TE ADA Inconclusive if $\geq 20\%$ of the patient's postbaseline samples, drawn predose, are ADA Inconclusive and all remaining postbaseline samples are ADA Not Present.

Treatment-emergent ADA negative (TE ADA-) patient: A patient who is evaluable for TE ADA is TE ADA- when the patient is not TE ADA+ and the patient is not TE ADA Inconclusive.

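### SAP 6.13.3 defines TE ADA- by exclusion, so two rare patient profiles with detected antibody are classed as treatment-emergent negative

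*SAP*

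**What the plan says.** SAP 6.13.3 sets four patient-level rules:

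- **Evaluable:** "the patient has a non-missing baseline ADA result, and at least 1 non-missing postbaseline ADA result". On what counts as missing, 6.13.2 says "In this context, 'missing' includes explicit 'ADA Missing' results". Inconclusive has its own row in Table 6.6 and is not named as missing.
- **TE ADA+, route a:** "The patient has baseline status of ADA Not Present and at least 1 postbaseline status of ADA Present with titer" of at least 2 x MRD (minimum required dilution). **Route b:** baseline Present and at least a 4-fold rise.
- **TE ADA Inconclusive:** at least 20% of the predose postbaseline samples are Inconclusive and "all remaining postbaseline samples are ADA Not Present".
- **TE ADA-:** "A patient who is evaluable for TE ADA is TE ADA- when the patient is not TE ADA" positive, with the second condition that the patient is not TE ADA Inconclusive either.

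Table 6.6 (SAP 6.13.1) calls a Not Detected sample Inconclusive if the drug level could interfere with the assay, "or drug concentration is planned per protocol but is not available". Its Not Present row covers some of the same ground. A Not Detected treatment-period sample with an unavailable planned concentration is Not Present, and patients on placebo are assumed to be below the drug tolerance level.

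SAP 6.13.4 uses these classes for the TE ADA+ proportion (denominator: evaluable patients), for the count of neutralizing antibody among TE ADA+ patients, for individual titer plots (TE ADA+ only), and for the summary of hypersensitivity and injection-site events by TE ADA status.

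**The concern.** A residual negative class is safe only if every patient with unresolved or positive evidence has been caught by the other classes first. Here that fails in two places.

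Neither TE ADA+ route starts from an Inconclusive baseline, so a strong seroconverter with that baseline cannot be counted as positive. Separately, the Inconclusive class is defeated by a single Present sample of any titer. Finding weak antibody in a patient whose other samples are largely uninterpretable therefore moves the patient towards negative, not away from it.

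At stake are the TE ADA+ proportion (first profile only) and the make-up of the TE ADA- column in the event summary (both profiles). That summary also drops detail: an event term seen in no TE ADA+ or TE ADA Inconclusive patient is reduced to a count of distinct terms. A term occurring only in a misfiled patient would lose its own row.

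**Working it through.** **Inputs.** The rules are those of SAP 6.13.1 to 6.13.3. The protocol's Schedule of Activities plans both an immunogenicity sample and a drug concentration at Visit 2. It gives 5 postbaseline immunogenicity samples in induction (V3-V7), 5 at V9-V17, 6 at V19-V29 and 2 in follow-up: 5 + 5 + 6 + 2 = 18. The 20% threshold is 0.20 x 18 = 3.6, so at least 4 of 18; for induction alone it is 0.20 x 5 = 1. The SAP states no Inconclusive rate and no expected TE ADA rate, so there is no figure of its own to reproduce.

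**Step 1: trace the profiles through the literal rules.** Titers are in MRD units and are illustrative.

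| Baseline | 18 postbaseline samples | Class |
|---|---|---|
| Inconclusive | all Present at 1024 x MRD | TE ADA- |
| Inconclusive | 1 Present at 1024 x MRD, 17 Not Present | TE ADA- |
| Inconclusive | all Inconclusive | TE ADA Inconclusive |
| Not Present | 17 Inconclusive, 1 Not Present | TE ADA Inconclusive |
| Not Present | 17 Inconclusive, 1 Present at 1 x MRD | TE ADA- |
| Not Present | 17 Inconclusive, 1 Present at 2 x MRD | TE ADA+ |
| Present at 4 x MRD | 17 Inconclusive, 1 Present at 8 x MRD (2-fold) | TE ADA- |
| Not Present | all Not Present | TE ADA- |

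**Step 2: enumerate.**

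- *Inconclusive baseline, at least one Present sample.* With i Inconclusive samples (0 to 18) and k Present (1 to 18 - i), there are 18 + 17 + ... + 1 = 171 count patterns. Five titer levels (1, 2, 4, 64 and 1024 x MRD) give 171 x 5 = 855 profiles. All 855 are TE ADA-.
- *Baseline Not Present, at least 4 of 18 Inconclusive, at least one Present at 1 x MRD.* There are 14 + 13 + ... + 1 = 105 patterns. All 105 are TE ADA-.

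**Step 3: ask when a baseline can be Inconclusive.** Interference is not expected before the first dose: no study drug has been given, and exclusion criterion 29 bars earlier biologics targeting IL-23 (with one named exception). What remains is a Not Detected sample with the planned Visit 2 concentration unavailable, in a patient randomized to LY3074828. The exemption in Table 6.6 closes this route only if Visit 2 counts as a treatment-period sample.

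**Step 4: size of the first profile.** Assume 1-5% of about 150 LY3074828 patients (3 arms x 50) lack the baseline concentration, 10-30% develop TE ADA, and the two are unrelated.

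- Low: 150 x 0.01 x 0.10 = 0.15 patients; 0.15/150 = 0.1 percentage points off the TE ADA+ proportion.
- High: 150 x 0.05 x 0.30 = 2.25 patients; 2.25/150 = 1.5 percentage points.

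**Step 5: size of the second profile.** These patients do not meet TE ADA+ under either wording, and they stay in the evaluable denominator. The effect on the TE ADA+ proportion is zero. Their number cannot be computed.

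**The case against.** The other side has several good points.

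- **The baseline route is narrow.** A reader might infer that every unavailable Visit 2 concentration creates the problem. It does not. A Detected sample is Present whatever the concentration, and the placebo rule gives placebo-arm samples a route to Not Present. The SAP also does not define a treatment-period sample for immunogenicity. SAP 6.1.2.1 starts induction on the date of first injection, and the protocol schedule places Visit 2 under induction dosing, so the exemption may be meant to apply. Against that, 6.13.2 calls samples up to the first dose baseline, and 6.12.4 separates baseline from treatment period. Both readings are open, which is itself a reason to clarify.
- **The first profile depends on Table 6.6.** This stands. Reconciling the table's missing-concentration wording would largely remove that profile without touching 6.13.3.
- **The second profile does not lower the TE ADA+ rate.** This also stands. A reader might infer that both profiles understate it, but patients in the second are below the SAP's own threshold. TE ADA- does not mean antibody-free.
- **Few patients are expected.** The SAP states that the assay's drug tolerance is high relative to peak drug levels and resolves missing treatment-period concentrations to Not Present.
- **Nothing is hidden.** A reader might infer that positive results disappear. SAP 6.13.4 lists all assessments, with titers, for anyone ever ADA Present, and lists their adverse events alongside. The listings do not, however, correct the summary tables, and they flag only samples that meet TE ADA+ criteria, which samples in the first profile cannot do.
- **No association test is planned.** The event summary is descriptive. A reader might put a size on a weakened link between antibody and events, but the documents give no event rate for these patients.

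**Conclusion.** The rule as written gives the wrong class for two profiles. This follows from the text alone, given that Inconclusive is not treated as missing.

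The first profile understates the TE ADA+ proportion by about 0.15 to 2.25 patients out of about 150. That range rests on assumed rates of 1-5% and 10-30%, neither of which is in the documents, and on Visit 2 falling outside the treatment-period exemption. If Visit 2 falls inside it, the first profile largely closes. The second profile leaves the TE ADA+ proportion unchanged and moves an unknown, probably small, number of unresolved patients into the TE ADA- column of the event summary.

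The severity is minor. ADA development is an exploratory objective (SAP 4.3), few patients are expected to be affected, and the primary endpoint does not depend on these classes.

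**What to change.** Two changes to the SAP:

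1. **Table 6.6 and 6.13.3.** State that a Not Detected sample taken before the first dose is ADA Not Present when its drug concentration is unavailable. In the same edit, reconcile the two rows of Table 6.6 so that an unavailable planned concentration leads to one result, not two.
2. **6.13.3.** Define TE ADA Inconclusive as at least 20% of postbaseline predose samples ADA Inconclusive, with TE ADA+ criteria not met. Delete the condition "all remaining postbaseline samples are ADA Not Present".

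Under these rules the first profile becomes TE ADA+ once a titer reaches 2 x MRD, and the second becomes TE ADA Inconclusive. The clear cases keep their class: all Not Present stays TE ADA-; one sample at 1 x MRD with the rest Not Present stays TE ADA-; baseline Not Present with a titer of at least 2 x MRD stays TE ADA+.

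The cost is a few sentences and a small change to the ADA derivation. A few patients may move from negative to positive or inconclusive.
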